3.2 BLINDING

All assessments will be conducted by blinded research associates. Due to the nature of the intervention, participants, their SPs, and care providers cannot be blinded.

4.0 STUDY ENDPOINTS AND COVARIATES

4.1 PRIMARY ENDPOINT

The primary outcome is the change in patient glycemic control from baseline to 6 months. Glycemic control is measured by HbA1c in %.

4.2 SECONDARY ENDPOINTS

Secondary outcome measures include the following:

- Change in HbA1c from baseline to 12 months
- Change in blood pressure from baseline to 6 months and to 12 months
 - Blood pressure will be measured by an automatic blood pressure monitor, taking the average of two readings taken 2 minutes apart. We will average the SBP at 6 months and 12 months and compare to SBP at baseline.
- Change from baseline to 6 months and to 12 months in diabetes distress in patient and in SP
 - The Problem Areas in Diabetes (PAID-5) Scale is comprised of 5 closed-ended items with response options ranging from 0 ('not a problem') to 4 ('serious problem'). The scale's 5 items will be summed to create a total score with a range of 0 to 20. A total score of ≥ 8 indicates possible diabetes-related emotional distress that warrants further assessment, with higher scores suggesting greater diabetes-related emotional distress.
- Change from baseline to 6 months in diabetes self-care behaviors in patient - including domains of diet, exercise, blood sugar testing, blood pressure checking, foot care and medication taking.
 - The Summary of Diabetes Self-Care Activities (SDSCA) is a brief self-report instrument for measuring levels of self-management across different domains of the diabetes regimen. Our study will score results within each domain by averaging the item scores (each ranging from 0-7) within each domain.
- Change from baseline to 6 months in self-efficacy of patient and of SP
 - The Self-Efficacy for Managing Chronic Diseases Scale is comprised of 5 items asking respondents to indicate how confident they are that they regularly can perform tasks related to their diabetes management. Responses range from 0 to 10, with higher numbers indicating greater self-efficacy.
- Change from baseline to 6 months in patient activation
 - The Patient Activation Measure (PAM)-10 uses a 4-point scale (1=strongly disagree to 4=strongly agree), where respondents indicate the extent to which statements related to being ready, willing and able to manage their health and health care accurately describe them. Responses are summed to create a total score with higher numbers indicating greater activation.
- Patient perceived overall satisfaction with SP support for diabetes from baseline to 6 months

- Items will assess patient's satisfaction with the support they receive from their SP and whether they feel like they would be worse off without their SP's help with their diabetes care. Responses will be rated on a 7-point scale (1=strongly disagree to 7=strongly agree). Responses are summed to create a total score with higher numbers indicating greater satisfaction.
- Patient perception of SP support from baseline to 6 months
 - Assessment will use the 8-item Important Other Climate Questionnaire (IOCQ) and non-supportive behaviors using 3 similarly-structured items addressing SP irritation, criticism and argumentativeness. All items are rated on a 7-point scale (1=strongly disagree to 7=strongly agree), with non-supportive behavior items being reversed scored.

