The University of Pittsburgh is providing local Investigators and study staff with offices/worksheets, desktop computers, access to computer servers and internet, high-volume printers, meeting rooms, and teleconferencing and video-conferencing hardware and software.

ACTIVITIES AT THE FEDERALLY QUALIFIED HEALTH CENTER

The intervention site will be an urban, community-based U.S. Federally Qualified Health Center (FQHC) in Detroit, Michigan, that serves a clientele that is majority Latino/a and Spanish-speaking. The FQHC will be responsible for all study procedures involving direct interactions with participants including recruitment, assessment and intervention.

OVERVIEW OF STUDY DESIGN

The study will be a single-site parallel arm randomized controlled superiority trial with dyads consisting of an adult with type 2 diabetes ('patient') and a selected family supporter ('support person'). Dyads will be randomized 1:1 to either the FAM-ACT program or a traditional individual patient-focused I-DSMES program for 6 months. Assessments of both members of the dyad will be conducted at approximately 6 and 12 months following enrollment. Figure 1 provides a graphic representation of the study protocol.

[figure not shown]

Figure 1. Overview of study design. Solid lines represent the standard protocol that all participants will follow; dotted lines represent an additional patient assessment that will be administered to patients whose 12-month assessment window opens while funding and resources still are available; T2D, type 2 diabetes mellitus; DSMES, diabetes self-management education and support; Dx, diagnosis; EMR, electronic medical record; FAM-ACT, Family Supporters for Health Action; SP, support person

RECRUITMENT, SCREENING, AND CONSENT

FQHC STUDY PATIENT CANDIDATE IDENTIFICATION AND CONTACT

Patients recruited by 'warm handoff' at the FQHC (FQHC clinical provider asks CHW or RA to meet with patient in person in clinic to describe the study) will receive study information in person at the FQHC by the CHW or RA.

Patients recruited from the recruitment flyer hanging in the FQHC, handed out at community health-related events, and posted on the FQHC Facebook, Twitter, and Instagram sites will contact the study staff via the phone number provided on the flyer.

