1. Take part in a one-hour introductory session designed to provide an overview of diabetes complications, how to set goals, and prepare for/participate in primary care appointments. During this session, the patient's diabetes complication risk profile will be discussed.
2. Be invited to 4-6 group diabetes self-management education sessions to be held at the FQHC or online using Pitt's HIPAA-compliant Zoom environment. In-person sessions at the FQHC will last approximately 1.5 hours whereas online sessions will be designed to last approximately 45 minutes. American Diabetes Association-approved 'Conversation Maps' will be used as a tool for patient education when feasible.
3. Complete an additional survey assessment and lab measures (blood pressure, weight and fingerstick blood HbA1c) with the study RA 6-months after enrollment. The SP will only complete one additional survey assessment 6 months after enrollment⁴. (*Some patients in both arms may be contacted 12-15 months post-enrollment to complete an additional assessment if the study still is active at the time that assessment window opens.*)
4. Receive care management contacts with a CHW every 2-4 weeks either in person or remotely (when necessary). The CHW will talk with the patient for approximately 20 minutes each time for the remainder of the 6-month enrollment period.
5. Patients who enrolled in the study prior to August 2020 will be contacted by phone for an additional, optional "FAM-ACT COVID" survey. The purpose of this survey is to determine how the events of the COVID-19 pandemic have affected patients' ability to participate in the intervention, and to care for their diabetes

PROGRAM B: SP-FOCUSED DSMES (FAM-ACT)

The FAM-ACT intervention will include patients and their SP together as much as possible. In this arm, the enrolled FQHC Patient and their SP (referred to as a dyad) will:

1. Take part in a one-hour introductory session designed to provide an overview of diabetes complications, ways the SP and patient can work together positively, and ways to set "SMART" health goals. During this session, results of a diabetes complication risk profile are discussed with the patient and support person and the dyad learns how to set goals together.

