2. Be invited to 4-6 family-focused, group diabetes self-management education sessions to be held at the FQHC or online using Pitt's HIPAA-compliant Zoom environment. In-person sessions at FQHC will last approximately 2 hours each, whereas online sessions will be designed to last approximately 1 hour. American Diabetes Association-approved "Conversation Maps" will be used as a tool for providing patient education when

⁴ In both arms, a +3 month assessment window will be permitted for both patient and SP assessments.

feasible. Additional family-focused topics will be discussed, such as patient-SP communication and SP roles in helping patients participate actively in healthcare provider appointments.

3. Complete additional survey assessments and lab measures (blood pressure, weight, fingerstick A1c, and lipids) with the study RA 6-months after enrollment. The SP will only complete one additional survey assessment 6-months after enrollment.
4. Receive care management contacts with a CHW every 2-4 weeks either in person or remotely (when necessary). The CHW will talk with the dyad for approximately 20 minutes each time for the remainder of the 6-month enrollment period.
5. Patients who enrolled in prior to August 2020 will be contacted by phone for an additional, optional "FAM-ACT COVID" survey. The purpose of this survey is to determine how the events of the COVID-19 pandemic have affected participants' ability to participate in the intervention, and to care for their diabetes

Additionally, the patient will have their FQHC electronic chart reviewed for diabetes-related visit, lab, and medication information for the period from 12 months prior to 24 months following their study enrollment date.

INTERVENTION PROCEDURES CONDUCTED IN BOTH STUDY ARMS

A trained and supervised CHW, CHW Manager, and/or RA at the FQHC will conduct all research participant contacts. Contacts at the FQHC will be supervised by the CHW Manager and Site PI. In-person diabetes self-management education group sessions will take place in a large conference room with other FQHC patients present. Online group sessions will be attended by study participants and the CHW(s). A study RA also may be present to assist with technical issues. Participant assessments will be completed in a private location at the FQHC or remotely via phone/video call or Zoom.

STUDY MEASURES

PATIENT MEASURES

Hemoglobin A1c (HbA1c)

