SP data will be measured via self-report survey, administered in-person or by phone by study RAs using the same method as patient surveys above, at baseline and 6-9 months post-baseline. Assessed constructs include psychological behavior determinants and SP roles in, behaviors relating to, and attitudes toward the patient's diabetes management. Select SP survey measures are presented in Table 2. As with the patient surveys, Spanish-language SP surveys were professionally translated.

Table 2. Select SP survey measures

MEASURE	CONCEPT CATEGORY	INSTRUMENT	BL	6M
Importance of diabetes	Competing factors	Single item: I have more important things in my life to take care of than helping <Patient> with their health care(5-point scale, 1-strongly disagree to 5-strongly agree)(12,13)	X	X
Self-efficacy for helping patient with diabetes	PBD	Self-Efficacy for Managing Chronic Diseases Scale (adapted for support person)(6,7)	X	X
Goal setting (help patient set goal)	SRBA	Adapted from Patient Assessment of Chronic Illness Care (PACIC) Goal setting subscale(8)	X	X
Supporter perception of patient empowerment	SRBA	DAWN Family Experience of Patient Involvement scale (DFEPI)(20)	X	X
Diabetes distress	SRBA	Problem Areas in Diabetes (PAID) - 5 for Family Members(4)	X	X
Caregiving burden	SP burden	DAWN Impact of Diabetes Profile - Family Members (DIDP-FM) plus additional question(20) ^a	X	X

BL, baseline; 6M, 6-month follow up; PBD, psychological behavior determinants; SP, support person; SRBA, SP roles, behaviors and attitudes

Bold typeface, measure will be examined as a secondary outcome (See Study Analysis Plan, SAP)

^aIn the last 6 months, how much of a burden has it been for you to help [Patient] manage their diabetes? (5-point scale: 1-very large burden to 5-no burden)

STATISTICAL CONSIDERATIONS

See Study Analysis Plan (SAP)

RISKS

POTENTIAL RISKS INVOLVED IN THIS STUDY

- Questionnaire assessments and collection of medical record information pose a risk for breach of confidentiality.
- Audiotaping of selected study procedures for fidelity monitoring purposes: it is possible that some participants may find being interviewed or audiotaped is stressful, and there is also a risk for breach of confidentiality.
- Fingersticks for HbA1c (FQHC Patients)
 - Patients may find these tests are uncomfortable, but the pain is typically minor and brief.

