Secondary outcomes: The original analysis plan included 6-month and 12-month change in patient UKPDS score as a secondary outcome. The calculation of UKPDS score is based on HbA1c, SBP, cholesterol levels, and smoking status.	Secondary outcomes: Change in UKPDS score has been dropped as a secondary outcome because patient cholesterol cannot be measured reliably without in-person assessment. A substantial number of first wave patients became eligible for their 6-month assessment while restrictions on in-person research activities were in effect.
SAMPLE SIZE	
See analysis plan	
DATA COLLECTION	
HbA1c: Per the original protocol, patients were to have their HbA1c assessed at 3 time points: baseline, 5 to 7 months post-baseline and 11 to 13 months post-baseline. All assessments were to be conducted by study RAs using the fingerstick method described above.	HbA1c: To accommodate pandemic-related restrictions on in-person research activities, 2 additional HbA1c assessment methods have been incorporated into the protocol. Clinic measures. Tests unable to be obtained in-person during the assessment window will be recorded from patients' EMRs rather than obtained via a study staff-conducted assessment. Home testing. Patients may be offered the option to self-test their HbA1c using a fingerstick device (e.g. A1cNow® Self Check, pts Diagnostics) sent to their home.
Survey assessments: As part of the original protocol, SPs were to be assessed by survey at 2 timepoints: baseline and 11-13 months post-baseline.	Survey assessments: Because the duration of the study protocol was decreased from 12 to 6 months, SPs now will be surveyed at baseline and 6-9 months post-baseline.

CHW, community health worker; DSMES, diabetes self-management education and support; EMR, electronic medical record; FAM-ACT, Family Support for Health Action; FQHC, Federally Qualified Health Center; HbA1c, hemoglobin A1c; I-DSMES, individual patient-focused diabetes self-management education and support; SBP, systolic blood pressure; SP, support person; UKPDS, UK Prospective Diabetes Study

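### The SAP lists 12-month support-person distress, but the current protocol schedules only one support-person follow-up survey, at 6-9 months

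*SAP*

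**What the plan says.** SAP section 4.2 names as a secondary endpoint "Change from baseline to 6 months and to 12 months in diabetes distress in patient and in SP". Section 5.3 plans contrasts at 6 and 12 months for secondary outcomes. Section 4.2 also lists SP self-efficacy, to 6 months only.

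The current protocol describes SP follow-up in several places:

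- Program A (I-DSMES), item 3: "The SP will only complete one additional survey assessment 6 months after enrollment".
- Program B (FAM-ACT), item 3: "The SP will only complete one additional survey assessment 6-months after enrollment".
- Footnote to the intervention arms: "a +3 month assessment window will be permitted for both patient and SP assessments".
- Support Person Measures: surveys "at baseline and 6-9 months post-baseline". Table 2 has baseline and 6-month columns only.
- Appendix 1, adapted column: "SPs now will be surveyed at baseline and 6-9 months post-baseline".
- Overview of Study Design, in the opposite sense: "Assessments of both members of the dyad will be conducted at approximately 6 and 12 months following enrollment".

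The Figure 1 legend and Program A item 3 describe the extra 12-month assessment for patients only, and only while the study is still active or funded.

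Appendix 1, in its original-protocol column, says that "SPs were to be assessed by survey at 2 timepoints: baseline and 11-13 months post-baseline". The section on COVID-19 adaptations says that protocol was used for the first 77 dyads, enrolled before March 2020. The adapted protocol took effect in February 2021.

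**The concern.** The SAP promises a 12-month SP result that the current schedule does not collect. An analyst following section 4.2 would find 12-month SP data, if any, only among the early dyads. Those dyads were enrolled before the pandemic into a 12-month intervention, whereas later dyads receive a 6-month intervention. For SPs, follow-up time and protocol version therefore largely coincide. A 12-month SP contrast would describe another intervention in a small subset, or would be a model extrapolation for everyone else.

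The 6-month SP endpoints (distress and self-efficacy) have the mirror-image gap, because the first 77 SPs appear to have had no survey planned at 6 months. The SAP has no rule for these SPs. Whether to drop, pool or relabel their values would be decided after the data are seen.

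**Working it through.** **The plan's own figures.** No sample size or power is given for SP outcomes. The HbA1c figures in SAP section 3.1 reproduce:

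- SD of change = 1.75 × √(2 × (1 − 0.6)) = 1.565.
- n per arm = 2 × 1.565² × (1.96 + 0.842)² / 0.6² ≈ 106.8, rounded up to 107; total 214.
- 214 / (1 − 0.20) = 267.5, rounded up to 268.

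They play no part in the problem except that 268 is the denominator below.

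**Scheduled SP follow-up by cohort, at planned enrolment**

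| Cohort | Dyads | 6-9 month SP survey | 11-13 month SP survey |
|---|---|---|---|
| Original protocol | 77 | none planned | planned |
| Adapted protocol | 268 − 77 = 191 | planned | none planned |
| Share of 268 | | 191/268 = 71.3% | 77/268 = 28.7% |

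On the schedules as written, no SP is due at both times.

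**Could the first 77 have moved to the 6-9 month schedule?** The latest of them enrolled at the end of February 2020 and passed 9 months at about the end of November 2020. The adapted protocol began in February 2021. A 6-9 month SP survey under that protocol is therefore unlikely for them. This is an inference from dates, not a record of what was done.

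**Does the window help?** The permitted extension takes 6 months to 9 months. The early SP window starts at 11 months. The wider-window strategy in SAP section 6.2 therefore does not bring the two together.

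**Illustration of size.** The documents give no SP attrition rate and no SD or effect size for SP distress. I take attrition between 0% and the 20% assumed for HbA1c, equal arms, 80% power and two-sided α = 0.05. The smallest detectable standardised difference is (1.96 + 0.842) × √(4/N).

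| SPs contributing | N at 0% loss | Detectable (SD) | N at 20% loss | Detectable (SD) |
|---|---|---|---|---|
| All dyads | 268 | 0.34 | 214 | 0.38 |
| Adapted cohort, 6-9 months | 191 | 0.41 | 153 | 0.45 |
| First 77, 11-13 months | 77 | 0.64 | 62 | 0.71 |

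At 20% loss, power for a 0.38 SD difference is 80% with all dyads, about 66% with the adapted cohort and about 32% with the first 77.

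**The case against.** **The protocol contradicts itself.** The overview sentence does say that both dyad members are assessed at about 6 and 12 months, so it is too strong to say simply that the protocol has no 12-month SP survey. This stands as a reason to correct the sentence. It does not rescue the endpoint: both arm descriptions, the SP measures section with its table, and Appendix 1 all give one survey, and the figure legend beside the sentence confines the extra assessment to patients.

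**The early schedule is a superseded plan.** A reader might infer that none of the first 77 SPs was surveyed at 6 months and that no SP has both values. The documents support this only as a schedule. Their 11-13 month windows fell during the pandemic, and actual survey dates are not reported. This objection stands in full.

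**The faulty model is assumed.** A reader might infer that the SAP will fit one slope joining two separate cohorts. That requires linear time to be chosen over categorical time, which section 5.2 leaves to fit criteria. It also requires section 5.3 to cover SP distress, although that section speaks of health behaviour and social support outcomes, and section 5.1 puts the main analyses at patient level. The documents do not settle either point.

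**Cohort differences are already examined.** Sections 5.4 and 6.4 compare enrolment before and after March 2020. That is true, but it creates no missing time point. For SP outcomes it also cannot separate enrolment period from follow-up time.

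**Restricting to the adapted cohort is not the only answer.** In both versions the SP survey falls around the end of the intervention, so a pooled end-of-intervention contrast is defensible. Dropping up to 29% of randomised dyads from SP comparisons is a real cost. This stands and shapes the fix.

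**Conclusion.** The inconsistency is real and confined to SP outcomes. As the documents stand, 12-month SP distress cannot be estimated for the trial as now run. Direct data could come only from the first 77 dyads, 29% of planned enrolment, under the 12-month intervention. The 6-month SP estimates can draw on at most the 191 planned later dyads, 71%.

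These counts rest on planned rather than achieved enrolment, and on the first 77 having kept their planned SP schedule. If some of them did have a 6-month survey, the 6-month gap shrinks. The 12-month endpoint would still have no scheduled data for the 191 later dyads. The counts of 153 and 62, and the detectable differences based on them, borrow the HbA1c attrition rate and are illustrations only.

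This does not touch the primary analysis or the sample size. SAP section 5.1 treats secondary outcomes as hypothesis generating. The point is worth correcting before analysis because the correction is cheap and removes a choice that would otherwise be made after seeing the data.

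**What to change.** 1. In SAP section 4.2, separate patient from SP distress. Define SP distress as change from baseline to 6 months, using the 6-9 month survey, and delete the 12-month SP endpoint. Protocol Aim 1 likewise lists distress, there for patients, as a 6-month change only.
2. Correct the protocol's design overview so that 12-month assessment applies to patients only and is conditional, as in the Figure 1 legend.
3. State in the SAP that SP values collected at 11-13 months in the first 77 dyads, for distress and self-efficacy, are not labelled or pooled as 6-month values. Report them separately, or prespecify a pooled end-of-intervention contrast stratified by protocol version as a supplementary analysis.
4. Record when the first 77 SPs were actually surveyed, and give the number of SPs contributing to each estimate.

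The cost is a wording change to both documents and one short rule in the SAP. No further data collection and no change to sample size are needed. The price is losing a nominal 12-month SP endpoint that the current schedule does not supply.

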5.0 STATISTICAL METHODS

5.1 GENERAL APPROACH

For all analyses, the overall level of significance will be set to $\alpha=0.05$. To achieve maximum power for the primary endpoint, and because analyses involving the secondary outcomes, mediation, and moderation are considered hypothesis generating, no adjustment for multiple testing will be used. Data analyses will be performed using SAS v9.4 (SAS Institute, Cary, NC) or the latest version of R (currently 4.2.2; <https://cran.r-project.org/>).

We will examine baseline data for prognostically important differences across the two study groups. All main outcome analyses will be conducted at the individual patient level, with treatment group as the primary grouping factor. Prior to hypothesis testing, data will be examined using standard univariate descriptive measures and bivariate statistical measures of association, as well as graphical displays. Statistical assumptions required for the methods of analysis outlined in this section will be rigorously tested. The failure of statistical assumptions necessary for the techniques planned will be addressed in one of the following ways: 1) a different method of analysis will be used (e.g., non-parametric tests versus parametric tests); or 2) the data will be appropriately transformed to a distribution that meets the assumptions of the proposed statistical test.

